### 4.2 PARTICIPANT DISPOSITIONS

The number (%) of participants included in each of the analysis populations listed in [Table 4](#) will be summarized.

Screen failures are defined as participants who consent to participate in the study but are not subsequently randomized. The number (%) of screen failures and reasons for screen failures will be provided in the screened population.

The number (%) of participants in the following categories will be provided:

- Randomized participants
- Randomized but not exposed participants
- Randomized and exposed participants
- Participants who completed the study treatment period as per protocol
- Participants who did not complete the study treatment period as per protocol and discontinued study treatment prior to Week 12 by main reason for permanent intervention discontinuation including due to COVID-19
- Participants who did not complete the study treatment period as per protocol and discontinued study treatment prior to Week 24 by main reason for permanent intervention discontinuation including due to COVID-19
- Participants who completed the study period as per protocol
- Participants who did not complete the study period as per protocol and discontinued study by main reason for study discontinuation including due to COVID-19.
- Vital status at last study contact

The number (%) of exposed and not randomized participants will also be summarized.

In addition, the number (%) of participants screened, screened-failed, randomized, with permanent intervention discontinuation and with early study discontinuation will be provided by country and site.

### Protocol deviations

Critical and major protocol deviations (automatic or manual) will be summarized in the randomized population and according to COVID-19 impact (i.e. deviations related to the COVID-19 pandemic and deviations not related to the COVID-19 pandemic). In addition, deviations potentially impacting the primary endpoint analysis will be summarized.

## **4.3 PRIMARY ENDPOINT(S) ANALYSIS**

### **4.3.1 Definition of endpoint(s)**

The primary endpoint for this study is the proportion of participants with improvement (reduction) in worst-itch numeric rating scale (WI-NRS) by  $\geq 4$  from baseline to Week 12.

WI-NRS is a patient-reported outcome (PRO) comprised of a single item rated on a scale from 0 (“No itch”) to 10 (“Worst imaginable itch”). Participants are asked to rate the intensity of their worst pruritus (itch) over the past 24 hours using this scale.

The weekly average WI-NRS score at each week, which is defined as the average of daily non-missing scores within the week window of each week (see [Section 5.4](#)), will be used for analyses.

For efficacy analysis, [Table 5](#) presents the prohibited and rescue medications/procedures which will be considered as intercurrent events if the last column indicates as “Yes” and therefore be handled in the estimands for endpoints defined in [Table 3](#).

**Table 5 - Prohibited medications/procedures and rescue medications that impact efficacy**

Medication/procedure	Comment	Data to be set as non-responder after taking medication in the main statistical analysis (Yes/No) a / Selection criteria
Prohibited medications/procedures		
Systemic immunosuppressive/immunomodulating drugs (eg, systemic corticosteroids, cyclosporine, mycophenolate-mofetil, interferon gamma, Janus kinase inhibitors, azathioprine, methotrexate, hydroxychloroquine, dapsone, sulfasalazine, colchicine, etc)	IMP to be discontinued	Yes (CDG b Immunosuppressant drugs Narrow and SDG b Corticosteroids Narrow )
Other monoclonal antibodies (that are biological response modifiers).	IMP to be discontinued	Yes (SDG b Monoclonal antibodies Narrow)
Phototherapy, including tanning beds.	IMP to be discontinued	Yes (CMQ b HLT Phototherapies, CMQ b Tanning_single PT)
Naltrexone or other opioid antagonist	IMP to be discontinued	Yes (SDG b Analgesia producing opioids NARROW)
Gabapentin, pregabalin, and thalidomide	IMP to be discontinued	Yes (CDG b Gabapentin mono and multi ingredients, Pregabalin mono and multi ingredients, or Thalidomide mono and multi ingredients)
Paroxetine, fluvoxamine or other SSRIs.	No IMP discontinuation, see requirement in the footnote	Yes c,d (CDG b N06AB selective serotonin reuptake inhibitors)
SNRIs.	No IMP discontinuation, see requirement in the footnote	Yes c,d (CDG b serotonin and norepinephrine reuptake inhibitors)
Amitriptyline or other tricyclic or tetracyclic antidepressants	No IMP discontinuation, see requirement in the footnote	Yes c,d (CDG b N06AA non-selective monoamine reuptake inhibitors)
Intralesional corticosteroid injections and cryotherapy.	No IMP discontinuation	Yes d (CMQ b Injection_single pt, cryotherapy or skin cryotherapy PT)
Sedating antihistamine	No IMP discontinuation	Yes d,e (CDG b sedating antihistamines)
Non-sedating antihistamine if used specifically for the treatment of itch secondary to AD or PN	No IMP discontinuation	Yes d,e (CDG b non-sedating antihistamines)

Medication/procedure	Comment	Data to be set as non-responder after taking medication in the main statistical analysis (Yes/No) a / Selection criteria
Rescue medications		
Dermatological preparations of high potency or superpotent TCS and TCI	No IMP discontinuation	Yes d (CDG b calcineurin inhibitors and corticosteroids narrow, Ticked 'RESCUE THERAPY' in CRF page)
a.	When yes, the estimand for the intercurrent event handling strategy will be as follows: hypothetical for continuous endpoints, and composite for responder and time-to-event endpoints. When no, a treatment policy strategy will be applied.	
b.	CDG=company drug groupings, CMQ=company MedDRA query, SDG= Standardized drug groupings.	
c.	Only if the antidepressant is initiated during the study or its dose is increased from baseline provided that medication was taken at least 3 months prior to screening.	
d.	As per medical adjudication, see Appendix 7 for details.	
e.	Only if the medication is initiated at Week 12 or Week 24, or the dose is increased from Week 11 to Week 12 or from Week 23 to Week 24.	

Blinded review of prohibited/rescue treatment (medication or procedure) based on [Table 5](#) and a pre-specified algorithm ([Appendix 7](#)) will be implemented before database locks by considering the type of medication or procedure, indication, timing, frequency and the potential impact of the use of the prohibited medications/procedures and rescue medications.

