### Medical conditions

- E 01. Presence of skin morbidities other than PN and mild AD that may interfere with the assessment of the study outcomes. Conditions such as, but not limited to, the following: scabies, insect bite, lichen simplex chronicus, psoriasis, acne, folliculitis, habitual picking, lymphomatoid papulosis, chronic actinic dermatitis, dermatitis herpetiformis, sporotrichosis, bullous disease.

NOTE: patients with mild active AD will represent up to 10% of the atopic PN study population.
- E 02. PN secondary to medications (eg, opioids, angiotensin converting enzyme [ACE] inhibitors).
- E 03. PN secondary to medical conditions such as neuropathy or psychiatric disease (eg, notalgia paresthetica, brachioradial pruritus, neurotic excoriations, obsessive compulsive disorder, delusions of parasitosis, etc).
- E 04. Patients with a documented AD severity moderate to severe within 6 months before the screening visit, or documented diagnosis of moderate to severe AD from screening visit to randomization visit (eg, IGA AD of 3 or 4, eczema area and severity index [EASI]  $\geq 16$ , scoring atopic dermatitis [SCORAD]  $\geq 25$ ).
- E 05. Severe concomitant illness(es) under poor control that, in the investigator's judgment, would adversely affect the patient's participation in the study. Examples include, but are not limited to patients with life expectancy shorter than 1 year, patients with uncontrolled diabetes (hemoglobin A1c  $\geq 9\%$  according to the laboratory results within 3 months before screening visit), patients with cardiovascular conditions (eg, Class III or IV heart failure according to the New York Heart Association classification), hepato-biliary conditions (eg, Child-Pugh Class B or C), neurological conditions (eg, demyelinating diseases), active major autoimmune diseases (eg, lupus, inflammatory bowel disease, rheumatoid arthritis, etc), other severe endocrinological, gastrointestinal, metabolic, pulmonary, or lymphatic diseases. The specific justification for patients excluded under this criterion will be noted in study documents (chart notes, eCRF, etc).
- E 06. Severe renal conditions (eg, patients with uremia and/or on dialysis).
- E 07. Participants with uncontrolled thyroid disease.

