## **6.5 CONCOMITANT THERAPY**

Any medication or vaccine (including over-the-counter or prescription medicines, vitamins, and/or herbal supplements) that the participant is receiving at the time of enrollment or receives during the study must be recorded along with:

- Reason for use.
- Dates of administration including start and end dates.
- Dosage information including dose and frequency.

The concomitant use of non-sedating antihistamine administration is allowed during the study except for treatment of AD or PN, but dose change of non-sedating antihistamine is not allowed both from Week 11 to Week 12 and from Week 23 to Week 24.

The concomitant use of the following therapies is prohibited during the entire study. Study treatment will need to be discontinued in participants receiving these treatments:

- Systemic immunosuppressive/immunomodulating drugs (eg, systemic corticosteroids, cyclosporine, mycophenolate-mofetil, interferon gamma, Janus kinase inhibitors, azathioprine, methotrexate, hydroxychloroquine, dapsone, sulfasalazine, colchicine, etc).
- Other monoclonal antibodies (which are biological modifiers).
- Phototherapy, including tanning beds.
- Naltrexone or other opioid antagonist.
- Gabapentin, pregabalin, and thalidomide.

The concomitant use of the following therapies is prohibited except if the dose has been stable for at least 3 months prior to screening, but study treatment will not need to be discontinued in participants receiving the treatments listed below. The dose should also remain stable (can be reduced or discontinued if medically indicated), but should not be initiated or increased throughout the study.

- Paroxetine, fluvoxamine, or other SSRIs.
- SNRIs.
- Amitriptyline or other tricyclic or tetracyclic antidepressants.

The concomitant use of the following therapies is also prohibited during the entire study, but study treatment will not need to be discontinued in participants receiving the treatments listed below.

- Intralesional corticosteroid injections and cryotherapy.
- Sedating antihistamine.
- Non-sedating antihistamine used specifically for the treatment of itch secondary to AD or PN.

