**Table 1 - Major changes in statistical analysis plan**

SAP Version	Approval Date	Changes	Rationale
1.0	04-Feb-2021	Not Applicable	Original version
2.0	Current version	
Add objective "To demonstrate efficacy of dupilumab on both itch as well as skin lesions within the same participant" and multicomponent endpoint (Proportion of participants with both an improvement (reduction) in WI-NRS by <math>\geq 4</math> from baseline to Week 24 and an IGA PN-S 0 or 1 score at Week 24) as a key secondary endpoint for the US and US reference countries hierarchy.
 
Add supplementary analysis (tipping point analyses) for primary and key secondary endpoints
 
Add subgroup analyses for key secondary endpoints.
 
Add subgroup analyses for participants who have been impacted (or not) by COVID-19
 
Modify hierarchical order for multiplicity procedure for US and US reference countries
 
Add as-observed plus multiple imputation supplementary analysis for the secondary endpoint (percent change from baseline in WI-NRS at Week 24)
 
Remove "selected" in the text including "selected prohibited and/or rescue medication"
	
To add this multicomponent endpoint as another measure of treatment success based on feedback from a health authority.
 
This additional supplementary analysis was recommended by a health authority to assess whether the estimate, and the inference thereof, was robust to departure from the strategies used in primary analysis for handling intercurrent events and missing data.
 
To evaluate whether the treatment effect is consistent across pre-specified subgroups on the key secondary endpoints in addition to the primary endpoint.
 
To address a health authority's request to assess the impact of the treatment effect by COVID-19.
 
To include the multicomponent endpoint in the hierarchy to address the health authority's feedback requesting assessment of this endpoint as another measure of treatment success.
 
To explore the robustness of the estimate, and the inference thereof, with a different strategy for handling intercurrent events and missing data
 
Since a participant who takes any protocol specified prohibited medications/procedures and/or rescue

SAP Version	Approval Date	Changes	Rationale
			medications is considered as a non-responder after medical adjudication/confirmation conducted in a blinded fashion, use of the word "selected" is confusing.

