#### 4.3.2 Main analytical approach

The primary estimand for the primary endpoint is the treatment policy/composite approach as defined in [Table 3](#).

The primary analysis population for the efficacy endpoints will be the ITT population.

The following null hypothesis H0 and alternative hypothesis H1 will be tested for dupilumab against placebo:

- H0: No treatment difference between dupilumab and placebo.
- H1: There is a treatment difference between dupilumab and placebo

The primary analysis will be conducted by using Cochran–Mantel–Haenszel test (CMH) test adjusted by documented history of atopy (atopic or non-atopic), stable use of TCS/TCI (yes or no), region, and baseline anti-depressant use (yes or no). Comparisons of the response rates between dupilumab and placebo will be derived. In addition, odds ratio and response rate difference as well as the corresponding 95% confidence intervals (CI) will be provided along with the p-values.

As defined in [Table 3](#) for participants discontinuing the study treatment before Week 12, their off-study treatment values measured up to Week 12 will be included in the analysis. Participants taking the prohibited medications/procedures and/or rescue medications (see [Table 5](#)) prior to Week 12 or having missing data at Week 12 will be considered non-responders.

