## 5.7 APPENDIX 7 MEDICATION/PROCEDURE ADJUDICATION ALGORITHM

### Algorithm for determining whether treatment with following medications or procedures constitutes treatment failure resulting in setting data as non-responder after taking medication or undergoing procedure in the main statistical analysis

1. Not required to adjudicate post-baseline medications (WHODD-coded) or procedures (CMQ-coded) as these will be considered treatment failures if used at any time.
  - a) Always considered treatment failure
    - ATC2 = CORTICOSTEROIDS FOR SYSTEMIC USE
    - ATC2 = IMMUNOSUPPRESSANTS (systemic, e.g. oral or parenteral route)
    - Preferred Drug Name = Ciclosporin
    - Preferred Drug Name = Methotrexate
    - Preferred Drug Name = Mycophenolate sodium
    - Preferred Drug Name = Mycophenolic acid
    - Preferred Drug Name = Azathioprine
    - Preferred Drug Name = Gabapentin
    - Preferred Drug Name = Pregabalin
    - Preferred Drug Name = Thalidomide
    - Preferred Drug Name = Lenalidomide
    - Preferred Drug Name = Baricitinib
    - Preferred Drug Name = Ruxolitinib
    - Preferred Drug Name = Tofacitinib
    - Preferred Drug Name = AbrocitinibPreferred Drug Name = Delgocitinib
    - Preferred Drug Name = Nalbuphine
    - Preferred Drug Name = Naltrexone
    - Preferred Drug Name = Naloxone
    - Preferred Drug Name = Vixarelimab
    - Preferred Drug Name = Nemolizumab
    - Preferred Drug Name = Serlopitant
    - Preferred Drug Name = Aprepitant
    - CMQb HLT Phototherapies
    - CMQ Tanning\_single PT

b) Never considered treatment failure:

- ATC2 = EMOLLIENTS AND PROTECTIVES
- ATC2 = GENERAL NUTRIENTS
- ATC2 = VITAMINS
- ATC2 = ANTIVIRALS FOR SYSTEMIC USE
- ATC2 = ANTIFUNGALS FOR DERMATOLOGICAL USE
- ATC2 = ANTISEPTICS AND DISINFECTANTS
- ATC2 = ANTIBIOTICS AND CHEMOTHERAPEUTICS FOR DERMATOLOGICAL USE
- ATC2 = ANTI-ACNE PREPARATIONS, excluding D10AA Corticosteroids, combinations for treatment of acne
- ATC2 = OPHTHALMOLOGICALS
- ATC1 = ANTIINFECTIVES FOR SYSTEMIC USE, excluding D07C Corticosteroids, combinations with antibiotics
- ATC1 = BLOOD AND BLOOD FORMING ORGANS
- ATC1 = ALIMENTARY TRACT AND METABOLISM
- ATC1 = MUSCULO-SKELETAL SYSTEM, excluding M01BA Antiinflammatory/antirheumatic agents in combination with corticosteroids
- ATC2 = COUGH AND COLD PREPARATIONS
- ATC2 = PSYCHOLEPTICS, excluding N05BB Diphenylmethane derivatives and N05C HYPNOTICS AND SEDATIVES

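### SAP Table 5 selects opioid antagonists with a grouping named for opioid analgesics, so a drug class the protocol does not prohibit could set a participant to non-responder

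*SAP*

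**What the plan says.** **Protocol.** Section 6.5 lists "Naltrexone or other opioid antagonist" among the therapies that are prohibited and require study treatment to stop. Exclusion criterion E18 and the prohibited list in SAP Appendix 3 also name antagonists. Opioids themselves appear only in exclusion criterion E02, as a cause of the disease: "PN secondary to medications (eg, opioids, angiotensin converting enzyme [ACE] inhibitors".

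**SAP Table 5.** The antagonist row is marked Yes, and its selection criterion is the standardized drug grouping "Analgesia producing opioids NARROW". The row does not carry footnote d (medical adjudication). The antidepressant, intralesional/cryotherapy, antihistamine and rescue rows do.

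**Consequence.** SAP 4.3.1 says Table 5 presents the medications and procedures "which will be considered as intercurrent events if the last column indicates as" Yes. Under SAP 4.3.2, participants with such use "prior to Week 12 or having missing data at Week 12 will be considered non-responders". Footnote a of Table 5 extends the rule to continuous and time-to-event endpoints.

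**Blinded review.** The text below Table 5 says a review based on both Table 5 and Appendix 7 "will be implemented before database locks by considering the type of medication or procedure, indication, timing, frequency" and potential impact. Appendix 7 is titled "Algorithm for determining whether treatment with following medications or procedures constitutes treatment failure resulting in setting data as non-responder". Item 1a, the automatic failures, names naltrexone, naloxone and nalbuphine as individual drugs. Item 2 adjudicates the other listed medications only when they are given for indications consistent with prurigo nodularis.

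**The concern.** The row label and the selector name point to different drug classes. An opioid analgesic is not an opioid antagonist, and the protocol does not prohibit opioid analgesics as concomitant medication. If the flag is built from the selector, people using a permitted drug for pain would count as failures at Week 12 and Week 24 whatever their itch or lesion result. Their continuous data would be set to missing and filled with the worst post-baseline value, and in the time-to-response analysis they would be censored at Week 24.

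This is a selection rule feeding the primary endpoint. A correction made after unblinding would be a post hoc change to responder status.

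**Working it through.** **1. One participant under each rule.** Take someone who uses an opioid analgesic, other than a drug named in item 1a, for pain before Week 12.

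| Rule | Outcome |
|---|---|
| Protocol 6.5; SAP Appendix 3 | Not a prohibited medication |
| Table 5 selector, read by its name | Flagged, hence non-responder; no footnote d |
| Appendix 7 item 1a | Not listed, so not an automatic failure |
| Appendix 7 item 2 | Not sent to adjudication: the visible indications are all dermatitis or eczema terms |

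The indication list is the last text available in the public copy and may continue. Footnote 1 of Appendix 7 requires a listing of classifications that depart from item 1. It requires none for departures from the Table 5 queries, so it would not clearly expose this mismatch.

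**2. Inputs for scale.** From protocol 9.2 and SAP 2: 56 per arm for 90% power, Fisher exact test, two-sided 0.05, 15% dropout, 75 per arm randomized. The response rates are redacted, so the 56 per arm cannot be reproduced.

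Assumptions:
- Placebo response is 5% to 30%, each rate paired with the dupilumab rate that gives 90% Fisher power at 56 per arm.
- A share q of each arm is misclassified, with q from 1% to 10%. The documents give no opioid-use rate.
- Use is independent of arm and of response.
- m is the share not already lost to missing data: 0.85 if all 15% dropouts count as non-responders, 1.00 if none do.

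**3. Formula.** Each response rate p becomes p × m × (1 − q), and the difference shrinks by the same factor. Exact Fisher power is then computed at 75 per arm. The expected number misclassified per arm is 75q: 0.75, 1.5, 3.75 and 7.5 for q = 1%, 2%, 5% and 10%.

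Example, 10% vs 36.6%, m = 0.85:
- q = 0: 8.5% vs 31.1%, difference 22.6 points, power 92.6%.
- q = 5%: factor 0.85 × 0.95 = 0.8075, giving 8.1% vs 29.6%, difference 21.5 points, power 90.8%.

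**4. Power (%) at 75 per arm, m = 0.85**

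| Placebo vs dupilumab | q=0 | 1% | 2% | 5% | 10% |
|---|---|---|---|---|---|
| 5% vs 28.2% | 93.7 | 93.4 | 93.1 | 92.1 | 90.2 |
| 10% vs 36.6% | 92.6 | 92.3 | 91.9 | 90.8 | 88.6 |
| 15% vs 43.7% | 92.1 | 91.7 | 91.3 | 90.1 | 87.7 |
| 20% vs 50.1% | 91.4 | 91.0 | 90.6 | 89.3 | 86.7 |
| 25% vs 56.4% | 91.4 | 90.9 | 90.4 | 88.9 | 86.2 |
| 30% vs 62.0% | 91.5 | 90.9 | 90.4 | 88.6 | 85.4 |

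**5. Power lost, in points (from unrounded values)**

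| | q=1% | 2% | 5% | 10% |
|---|---|---|---|---|
| m = 0.85 | 0.3–0.5 | 0.6–1.1 | 1.6–2.8 | 3.5–6.1 |
| m = 1.00 | 0.2–0.3 | 0.3–0.5 | 0.9–1.5 | 2.1–3.4 |

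These figures use the unstratified Fisher test of the sample-size section, not the stratified CMH test of the primary analysis.

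**The case against.** The best defence is that the selectors are search nets and the blinded review sets the flag.

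- SAP Table 1 says a user of a protocol-specified prohibited or rescue medication "is considered as a non-responder after medical adjudication/confirmation conducted in a blinded fashion". An opioid analgesic is not protocol-specified.
- The Appendix 7 title claims the non-responder decision, and the review below Table 5 must weigh indication.
- Rows without footnote d broadly match the classes in item 1a, so its absence may only mean automatic failure by drug name.
- Read literally, the corticosteroid selector, which has no route limit, could flag the low-to-medium potency topical steroids that protocol 6.1.1 allows as background. Item 1a restricts corticosteroids to systemic use, which suggests the queries were meant to be refined.
- The grouping's members are not given; Table 14 lists only conjunctivitis and immunoglobulin groupings.

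Most of this stands as mitigation. If Appendix 7 decides status, no harm follows, and naltrexone and naloxone are caught by name in any case. But no sentence gives Appendix 7 precedence over the Table 5 query, while the primary-analysis text, the estimand table and the time-to-event rule all refer to Table 5 for the event. The corticosteroid example shows that precedence needs stating more widely; it does not make the opioid selector right. The unknown membership limits how far the consequence can be asserted, and the sponsor can settle it by opening the grouping.

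The objection that the opioid-use share is wholly assumed is also fair. So is the point that off-treatment data are retained, so not every dropout becomes a non-responder. The figures are therefore given as ranges, including m = 1.00.

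**Conclusion.** The concern holds and is minor. The selection criterion is wrong on its face for its row, and two operational definitions of the same event coexist with no stated order. Misclassification is conditional on the query setting the flag and on the grouping containing what its name says. Whether the grouping misses antagonists cannot be determined from the documents.

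Under equal use in both arms, the error shrinks the treatment difference and does not create a false positive. Across the assumed scenarios the lowest power is 88.6% at q = 5% and 85.4% at q = 10%. The as-observed supplementary analysis (SAP 4.3.4, extended to the key secondary endpoints by SAP 4.4.1.2) would show the result without the non-responder rule for medication use.

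**What to change.** While blinded and before database lock:

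1. Replace the selector in the antagonist row of Table 5 with an opioid-antagonist grouping, or a named drug list, that agrees with the row label, protocol 6.5 and Appendix 7 item 1a.
2. Add a sentence to SAP 4.3.1 stating that the blinded Appendix 7 classification determines the final flag when it differs from a Table 5 query.
3. Re-run the medication flag and list every participant whose status changes.

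The cost is one table cell, one sentence and one re-run. Participants and sites are not affected.

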#### **Prior/concomitant therapy**

- E 17. Exposure to another systemic or topical investigative drug (monoclonal antibodies as well as small molecules) within a certain time period prior to Visit 1 (screening), as follows: an interval of less than 6 months or <5 PK half-lives for investigative monoclonal antibodies, whichever is longer, and an interval of less than 30 days or <5 PK half-lives, whichever is longer, for investigative small molecules.
- E 18. Having used any of the following treatments within 4 weeks before the screening visit
  - Systemic immunosuppressive/immunomodulating drugs (eg, systemic corticosteroids, cyclosporine, mycophenolate-mofetil, interferon gamma, Janus kinase inhibitors, azathioprine, methotrexate, hydroxychloroquine, dapsone, sulfasalazine, colchicine, etc).
  - Intralesional corticosteroid injections and cryotherapy.
  - Phototherapy, including tanning beds.

- Naltrexone or other opioid antagonist.
- Gabapentin, pregabalin, and thalidomide.

Or starting to use the following treatments or changed the dose of the following treatments in 3 months before the screening visit or expected the dose of the following treatments will be changed throughout the study:

- Paroxetine, fluvoxamine, or other selective serotonin reuptake inhibitors (SSRIs).
- Serotonin and norepinephrine reuptake inhibitors (SNRIs)
- Amitriptyline or other tricyclic or tetracyclic antidepressants.

E 19. Previous treatment with biologic medicines within the following timeframe:

- Any cell-depleting agents including but not limited to rituximab: within 6 months before the screening visit.
- Omalizumab: within 5 months before screening visit.
- Other immunomodulatory biologics: within 5 half-lives (if known) or 16 weeks before the screening visit, whichever is longer.

E 20. Initiation of treatment with prescription moisturizers or moisturizers containing additives such as ceramide, hyaluronic acid, urea, menthol, polidocanol, or filaggrin degradation products during the screening period (patients may continue using stable doses of such moisturizers if initiated before the Screening visit).

E 21. Initiation of treatment with TCS/TCI (any potency) during the screening period or treatment with high potency or superpotent TCS/TCI during the screening period.

E 22. For participants who were on a stable regimen of TCS/TCI (maintain same medicine, same dose from 2 weeks prior to screening visit) at the screening visit:

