#### *Observation period*

The observation period will be divided into 4 segments:

- The **pre-treatment period** is defined as the period up to first IMP administration.
- The **treatment-emergent (TE) period** is defined as the period from the first IMP administration to the last IMP administration + 98 days. The treatment-emergent period includes the following 2 periods:
  - The **on-treatment period** is defined as the period from the first IMP administration to the last administration of the IMP + 14 days
  - The **residual treatment period** is defined as the period from the end of the on-treatment period to the end of the treatment-emergent period.
- The **post-treatment period** is defined as the period from the end of the treatment-emergent period.

The on-study observation period is defined as the time from start of intervention until the end of the study defined as the status date collected on e-CRF page “Completion of End of Study”.

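### SAP Table 5 footnote c counts an on-study antidepressant dose increase as an intercurrent event only after 3 months of use before screening, a condition that Protocol 6.5 does not contain

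*SAP*

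**What the plan says.** SAP Table 5 (section 4.3.1) lists the prohibited and rescue treatments that are handled as intercurrent events. The three antidepressant rows (SSRIs, SNRIs, tricyclics and tetracyclics) are marked Yes, subject to footnotes c and d, with the comment "No IMP discontinuation, see requirement in the footnote". Footnote c begins "Only if the antidepressant is initiated during the study or its dose is increased from baseline" and attaches to the dose-increase route the condition "provided that medication was taken at least 3 months prior to screening", so that this route reads in full: "its dose is increased from baseline provided that medication was taken at least 3 months prior to screening". Footnote d sends these rows to medical adjudication under Appendix 7. Footnote a sets a composite strategy for responder and time-to-event endpoints and a hypothetical strategy for continuous endpoints where the answer is Yes, and treatment policy where it is No.

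Protocol 6.5 says that these drugs are "prohibited except if the dose has been stable for at least 3 months prior to screening", and that they "should not be initiated or increased throughout the study". Exclusion criterion E18 bars entry for recent use: "Or starting to use the following treatments or changed the dose of the following treatments in 3 months before the screening visit". SAP Appendix 3 repeats the 3-month stability rule and the bar on increases. The SAP version history explains that the word *selected* was removed because taking any prohibited medication specified in the protocol makes a participant a non-responder once blinded adjudication confirms it.

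**The concern.** In the protocol, the 3-month period settles who may be on an antidepressant at entry. In footnote c the same period settles whose dose increase counts. Moving it there leaves a gap for the participant whose use was least acceptable to begin with: a recent starter, randomized in deviation from E18, whose dose then goes up during treatment.

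At stake is consistent classification. Two participants with the same increase before Week 12 could be treated differently on the primary endpoint, one as a non-responder and the other on the observed WI-NRS, because of how long each had used the drug before screening. Table 5 also feeds the key secondary, time-to-event and continuous endpoints, so the inconsistency carries through to all of them. Its title describes the listed treatments as affecting efficacy, and the protocol amendment added baseline antidepressant use as a covariate because of its possible impact on the treatment effect. The sponsor therefore regards these drugs as relevant to the outcome.

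**Working it through.** The plan gives no figure to reproduce here. The check is to apply footnote c as a rule and compare the result with the protocol.

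**Reading the footnote.** Its opening words make it a necessary condition. There are two routes to an event: (i) initiation during the study; (ii) an increase from baseline, given 3 months of use before screening. The proviso can sensibly attach only to route (ii), since a drug started on study cannot have been taken before screening.

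**Case by case, before adjudication:**

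1. Started during the study. Route (i) is met, so it counts. Protocol 6.5 bars it. Consistent.
2. On the drug at least 3 months before screening, dose raised on study. Route (ii) is met, so it counts. Protocol 6.5 bars it. Consistent.
3. On the drug at least 3 months with a stable dose, unchanged or reduced on study. Neither route is met. Protocol 6.5 allows it. Consistent.
4. Started less than 3 months before screening, dose raised on study. Route (i) fails because the start came before the study; route (ii) fails on the proviso. It does not count, although Protocol 6.5 bars the increase. **Inconsistent.**
5. Started less than 3 months before screening, dose unchanged. Neither route is met. E18 and Protocol 6.5 do not permit this use, and footnote c does not say how it is classified. **Unaddressed.**

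The gap is confined to recent starters. Someone on the drug for 3 months or longer who changed dose within the 3 months before screening is also barred by E18, but a later increase in that person meets route (ii).

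**Does case 4 stay in the analysis?** Yes. The efficacy population is ITT, meaning all randomized participants (SAP section 3, Table 4), so an E18 deviation does not remove anyone. With the footnote's condition unmet, footnote a points to treatment policy, that is, data as observed.

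**Scale.** Planned arm size is 75 (SAP 1.1). One participant counted as a responder instead of a non-responder shifts that arm's rate by 1/75 = 0.0133, or 1.3 percentage points. A case 4 participant who does not reach the 4-point WI-NRS reduction shifts nothing. Within the arm the shift is upward; its effect on the treatment difference depends on which arm the participant is in, and the documents give no basis for predicting that.

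**The case against.** The best defence has three parts.

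First, the affected group should be close to empty. E18 excludes recent starters and the protocol allows no waivers. A changed result needs an entry deviation, then a barred increase before the endpoint, then a WI-NRS response, then adjudication that does not call failure. Deviations that could affect the primary endpoint are to be summarized (SAP 4.2), and baseline antidepressant use is both an adjustment factor and a subgroup. This stands, and it is why the point is small.

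Second, adjudication may catch the case. A reader might infer from footnote c that such increases never count. The documents do not support that. Appendix 7 tells adjudicators to weigh dose, timing, indication and likely impact as well as the Table 5 criteria, and it allows an additional blinded review of all post-baseline medications. What remains is that required adjudication covers only indications consistent with PN, that it carries the Table 5 criteria forward, and that no rule in it restores case 4.

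Third, the proviso may only be loose drafting meant to separate established background use from new use. A reader might go further and say that the SAP reverses the protocol. That is too strong: Protocol 6.5 governs what participants may take and leaves the event definition to the SAP, and Appendix 3 restates the protocol's rule. The problem is a misplaced condition, but a programmer applying it literally would drop the event.

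A reader might also infer that a start between screening and Day 1 escapes footnote c, because the SAP says "The on-study observation period is defined as the time from start of intervention until the end of the study". That is a definition of a different term. SAP 1.1 includes the screening period in the study duration, so on the plain reading a start during screening already falls under route (i).

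**Conclusion.** The point holds in a narrow form. As worded, footnote c does not count a dose increase in a participant who started the antidepressant less than 3 months before screening. This is inconsistent with Protocol 6.5, with SAP Appendix 3 and with the intent stated in the SAP version history. Such a participant is analysed as observed unless blinded adjudication decides otherwise.

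Materiality is very small. The documents give no count of such participants, and it may be zero; no percentage can be put on it from the text. The only supportable measure is 1.3 percentage points in one arm for each misclassified participant, assuming 75 per arm, with unknown direction for the treatment difference. No sample size or power figure is affected. The conclusion rests on a literal reading of the footnote and on at least one E18 deviation among those randomized.

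**What to change.** In SAP Table 5 footnote c, keep the words "Only if the antidepressant is initiated during the study or its dose is increased from baseline" and replace the proviso with a statement that this applies regardless of prior duration of use. Keep adjudication under footnote d. Add a sentence saying how baseline antidepressant use that E18 and Protocol 6.5 do not permit is classified when the dose does not change (case 5), since deleting the proviso does not settle that.

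The initiation route should stay as worded. Extending it to any start after the screening visit would add a rule turning a pre-randomization start into non-response, which goes beyond reconciling the two documents.

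The cost is one footnote and one sentence, made before database lock and while the review is still blinded. Protocol 6.5 already requires dates and doses of concomitant medications to be recorded, so no new data are needed. The change affects analysis classification only, not how participants are managed.
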